10.9.4 Nevi Evaluation

Nevi will be assessed at the specified timepoints shown in the schedule of assessments (Table 9-1). Baseline nevi evaluation will be conducted at any time (Visit 1 or 2) before randomization.

Nevi will be assessed locally by a visual full body examination performed by a dermatologist or other qualified site staff. Any subject with suspicious nevi of clinical concern will have treatment temporarily discontinued and be referred for further nevi evaluation (e.g., biopsy), as deemed necessary by the dermatologist or other qualified site staff.

Any biopsy samples collected during the study will be sent for evaluation to the central pathology lab. If there are any clinically significant adverse findings from the biopsy, subjects will not be allowed to resume study drug and will be discontinued from study treatment. Adverse change must be demonstrated histologically and confirmed by central pathologist. Visual evaluation of change will not be acceptable criteria for complete discharge from treatment. If central assessment determines that lesion or nevi is benign, and the findings are not clinically significant, subject will be allowed to resume study treatment at the same dose when study drug was interrupted. Clinical sites will have access to a centralized dermatology specialist with experience on nevi. The centralized dermatology specialist will be available to communicate with the Investigator, dermatologist and/or qualified staff on the changes of any expected potential changes in nevi and advice on the process management prior and after biopsy.

The results will be recorded in the source documents and the eCRF as well as shared and discussed with the subject. Nevi of clinical concern must be recorded as AE.

Nevi assessment details will be fully described in a separate document.

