The number of subjects with post-baseline assessments $\geq 2 \times$ ULN and $\geq 3 \times$ ULN and so on will be calculated for ALT, AST, GGT, ALP, direct and total bilirubin and summarized by treatment group for each post-baseline visit.

The figure of mean (or median) and standard error value of ALT, AST, total bilirubin and alkaline phosphatase by visit will be plotted.

Vital signs and electrocardiogram data

Vital signs and 12-lead ECG variables and changes from baseline will be descriptively summarized at each visit by treatment group.

The baseline for the vital sign parameters and 12-lead ECG measurements will be the last valid assessment obtained on Day 1 prior to the administration of double-blind treatment period.

For ECGs, number and percentage of subjects meeting the criteria listed below will be presented in tables:

- Baseline Corrected QT interval (QTc) <450 msec and >500 msec at EOT
- Baseline QTc <450 msec and 500 msec \geq QTc > 480 msec at EOT
- Baseline QTc <450 msec and 480 msec \geq QTc > 450 msec at EOT
- Increase from baseline at EOT in QTc > 30 msec
- Increase from baseline at EOT in QTc > 60 msec

These criteria will be applied to both Corrected QT interval using Bazett's formula (QTcB) and Corrected QT interval using Fridericia's formula (QTcF).

Physical examination and Nevi evaluation

Physical examination data will be summarized descriptively (number and percentage of the subjects) in tables by treatment and time point.

Nevi appearance will be summarized descriptively (number and percentage of the subjects) in tables by treatment and analysis visit for subjects' suspicious nevi found.

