6 STATISTICAL CONSIDERATIONS

6.1 Descriptive Statistics

Continuous data will be summarized descriptively using the number in the analysis set (N), the number of observations (n), mean, standard deviation (SD), median, minimum and maximum. Categorical data will be summarized using frequency counts and percentages. The denominator for the percentages will be the total number of subjects in the treatment group and analysis population being presented, unless otherwise specified (e.g. on some occasions, percentages may be calculated out of the total number of subjects with available data at a particular visit and/or time point).

Unless otherwise specified, all data will be summarized by analysis visits and treatment group.

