7.2.3 Safety Assessments

7.2.3.1 Adverse Events

Adverse events will be coded according to the MedDRA version 23.1.

(1) Treatment Emergent Adverse Events/ Treatment Emergent Serious Adverse Events (TEAEs/TESAEs)

AEs will be classified as ‘treatment-emergent’ if they arise following the first administration of study medication in the treatment period (after randomization) or if a pre-dose AE increases in severity following dosing in the treatment period (after randomization).

Rule to determine TEAE using onset date of AEs:

An AE is classified as treatment emergent if it newly occurred on or after the first dose of study drug. According to this data handling, for the severity part in the above TEAE definition, the AE with upgraded severity and with the new onset date during the treatment period will be automatically included as TEAE.

(2) Adverse Event Related to Study Drug

A TEAE is considered “adverse event related to study drug” if it has been assessed as having a “reasonable possibility” in relationship to the study drug.

(3) Duration of Adverse Events

Duration of Adverse Events (days) = AE stop date – AE start date + 1.

(4) Time to AE onset

For DBT period, time to AE onset (days) = AE start date – the first treatment date in DBT period + 1.

For DBE period, time to AE onset (days) = AE start date – the first treatment date in DBE period + 1.

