7.2.3.3 Laboratory Tests

(1) Criteria for pre-defined limit

Liver function:

- ALT $\geq 10 \times \text{ULN}$
- $8 \times \text{ULN} \leq \text{ALT} < 10 \times \text{ULN}$
- $5 \times \text{ULN} \leq \text{ALT} < 8 \times \text{ULN}$
- $3 \times \text{ULN} \leq \text{ALT} < 5 \times \text{ULN}$
- $1 \times \text{ULN} \leq \text{ALT} < 3 \times \text{ULN}$

The above same criteria will be applied to AST.

- Total Bilirubin $\geq 2 \times \text{ULN}$
- $1 \times \text{ULN} \leq \text{Total Bilirubin} < 2 \times \text{ULN}$

7.2.3.4 12-Lead ECG

(1) Criteria for pre-defined limit

12-lead ECG:

- Baseline QTc $< 450 \text{ msec}$ and $> 500 \text{ msec}$ at any post baseline
- Baseline QTc $< 450 \text{ msec}$ and $500 \text{ msec} \geq \text{QTc} > 480 \text{ msec}$ at any post baseline
- Baseline QTc $< 450 \text{ msec}$ and $480 \text{ msec} \geq \text{QTc} > 450 \text{ msec}$ at any post baseline
- Increase from baseline in QTc $> 30 \text{ msec}$, 60msec at any post baseline

The above same criteria will be applied to QTcF and QTcB.

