Week 26 (DBE Baseline)	Day 183	Day 134 to 202
Week 39	Day 274	Day 250 to 320
Week 52 (DBE EOT)	Day 365	Day 321 to 396
Follow-up until Week 32 (DBT EOS)	6 weeks after EOT for DBT	NA
Follow-up until Week 58 (DBE EOS)	6 weeks after EOT for DBE	NA

(3) Safety data

Table 4 Analysis Visit Window for safety data

Analysis Visit	Nominal day	Analysis Visit Window
Screening*	Day -42*	-
Baseline*	First dose day*	NA*
Week 2	Day 15	Day 2 to 22
Week 4	Day 29	Day 23 to 42
Week 8	Day 57	Day 43 to 71
Week 12	Day 85	Day 72 to 119
Week 16 (Only for Norway site)	Day 113	-
Week 18(Only for Japan and Canada site)	Day 127	-
Week 20 (Only for Norway site)	Day 141	-
Week 26 (DBT EOT)	Day 183	Day 134 to 190

Week 26 (DBE Baseline)	Day 183	Day 134 to 190
Week 28	Day 197	Day 191 to 211
Week 30 (Only for Germany site)	Day 211	-
Week 32	Day 225	Day 212 to 249
Week 36 (Only for Norway, Germany and Canada site)	Day 253	-
Week 39	Day 274	Day 250 to 320
Week 43 (Only for Norway site)	Day 302	-
Week 47 (Only for Norway site)	Day 330	-
Week 52 (DBE EOT)	Day 365	Day 321 to 396
EOT for DBT (LOCF)	Day 182 or discontinued during DBT	The latest visit during DBT period
EOT for DBE (LOCF)	Day 365 or discontinued during DBE	The latest visit during DBE period
Follow-up until Week 32 (DBT EOS)	6 weeks after EOT for DBT	NA
Follow-up until Week 58 (DBE EOS)	6 weeks after EOT for DBE	NA

* For liver function markers (ALT, AST, GGT, ALP, direct and total bilirubin), the mean value of two numerical values at screening visit and at randomization visit (the first dose day) will be treated as a baseline value.

The date of the first dose of study drug is defined as Day 1.

Unless otherwise specified, baseline will be the last observed value of the parameter of interest prior to the first intake of study drug (for DBT) or will be the available value of parameter of Week 26 (for DBE).

For other visits, if there are multiple data in a window, the closest data to nominal day will be used. If the distance to the nominal day is the same, the data of later date will be used.

According to country specific protocol for Japan, Norway, Germany and Canada, liver function markers (ALT, AST, GGT, ALP, direct and total bilirubin) will be measured at each country specific visit in each country.

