8.3.2 Laboratory Tests

Absolute values and changes from baseline will be summarized for the following laboratory tests parameters. For Haemoglobin, Haematocrit, Red Blood Cell, MCV, Alkaline phosphatase, Aspartate aminotransferase, Alanine aminotransferase, Gamma glutamyl transpeptidase and Bilirubin (direct and total), absolute values and changes from baseline will be summarized by region (North America, Europe, Japan, Australia). Standard Unit will be used for the summary.

Laboratory Test	Parameters
Hematology	Haemoglobin, Haematocrit, Red Blood Cell, Platelet count, MCV, MCH, MCHC, White blood cell count and differential
Biochemistry	Alkaline phosphatase, Aspartate aminotransferase, Alanine aminotransferase, Gamma glutamyl transpeptidase, Potassium Sodium, Chloride, Inorganic phosphate, Glucose, Bilirubin (direct and total), Blood urea nitrogen, Cholesterol, Triglycerides, High density lipoprotein cholesterol, Low density lipoprotein cholesterol, Protein (total), Albumin, Creatine kinase, Creatinine, Ferritin, Vitamin D
Coagulation	PT, INR, aPTT
Urinalysis	Specific gravity, pH, protein, glucose, ketones, urobilinogen, blood Microscopic examination ^a

^aPerformed only if required, based on urinalysis results

Shift table of clinically relevant categories will be presented for the following laboratory tests parameters. The categories will be Low, Normal and High for Hematology, Biochemistry, Urinalysis and Coagulation, and Normal and Abnormal for Urinalysis (Qualitative Value).

A shift table of the number and percentage will be provided for subjects who had any post baseline maximum value at any time during the treatment period and met the liver function tests (AST, ALT and Total bilirubin) criteria of the pre-defined limit for the maximum value.

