8.3.6 Nevi appearance

Nevi appearance will be summarized with the number and percentage of the subjects' suspicious nevi found:

- Any suspicious nevi found during assessment (Y,N)
- Any clinically significant findings (Y,N).

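### Nevi findings are tabulated by visit only, so the plan never counts subjects who ever had a suspicious nevus, and a positive exam can be missing from the nevi table

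*SAP*

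**What the plan says.** SAP 8.3.6 asks for the number and percentage of subjects on two yes/no items: whether any suspicious nevus was found, and whether any finding was clinically significant. The section does not mention visits. The by-visit layout comes from three other places:

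- SAP 6.1 sets the default: "Unless otherwise specified, all data will be summarized by analysis visits and treatment group".
- Protocol 14.3.3 says: "Nevi appearance will be summarized descriptively (number and percentage of the subjects) in tables by treatment and analysis visit".
- SAP 9.3 marks nevi at Screening, Weeks 4, 12 and 26, EOT (LOCF) and follow-up for the double-blind treatment period (DBT). For the extension (DBE) it marks Week 26 (DBE Baseline), Weeks 39 and 52, EOT (LOCF) and follow-up. Weeks 2, 8, 28 and 32 carry laboratory entries only.

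SAP 7.3, Table 4, assigns safety records to visits. When a window holds more than one record, "if there are multiple data in a window, the closest data to nominal day will be used", with the later date breaking a tie. The EOT (LOCF) rows use the latest visit in the period.

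Other safety measures get an any-time summary. SAP 8.3.2 plans a liver-test shift table for "subjects who had any post baseline maximum value at any time during the treatment period". The QTc criteria in SAP 7.2.3.4 end with "60msec at any post baseline".

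**The concern.** The usual safety question is how many subjects in each arm ever had the finding. By-visit rows cannot answer it. One subject positive at both Weeks 4 and 12 gives the same two row counts as two subjects positive once each.

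In addition, a positive exam can drop out of the table altogether, because neither the closest-record rule nor the latest-record rule looks at the result. That can happen in three ways: another record in the same window lies closer to the nominal day, the exam falls on a day with no nevi row, or Visit 4 takes place on Day 22. At stake is whether one descriptive table shows the per-arm incidence of suspicious nevi for a drug that stimulates melanin production.

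**Working it through.** No sample size, power or alpha figure is involved. The check maps exam days to table rows.

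**Scheduled exams.** The allowed days come from protocol Table 9-1 (nominal day ±7, so 15 days each) and the windows from SAP Table 4.

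| Visit | Allowed days | Window for that visit | Allowed days outside |
|---|---|---|---|
| 4 | 29±7 = 22–36 | Week 4: 23–42 | 1 of 15 (Day 22) |
| 6 | 85±7 = 78–92 | Week 12: 72–119 | 0 of 15 |
| 7 | 183±7 = 176–190 | Week 26: 134–190 | 0 of 15 |
| 10 | 274±7 = 267–281 | Week 39: 250–320 | 0 of 15 |
| 11 | 365±7 = 358–372 | Week 52: 321–396 | 0 of 15 |

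Day 22 lies in the Week 2 window (Day 2 to 22), and Week 2 has no nevi entry in SAP 9.3. This case comes from the window boundary, not from the closest-record rule.

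**Days with no nevi visit row.**

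- DBT: Days 2–22 (Week 2), 43–71 (Week 8) and 120–133 (no window). That is 21 + 29 + 14 = 64 of the 189 days from Day 2 to Day 190.
- DBE: Days 191–211 (Week 28) and 212–249 (Week 32). That is 21 + 38 = 59 of the 206 days from Day 191 to Day 396. For the extension analysis, Days 183–190 map to the DBE Baseline row, so they have no post-baseline row either.

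These are shares of days, not of exams. Scheduled exams fall almost entirely inside the nevi windows.

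**Displacement inside a reported window** (distance from nominal day; the smaller one is kept).

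- Positive on Day 100, negative on Day 85: |100 − 85| = 15 against 0, so Week 12 shows negative.
- Positive on Day 150, negative on Day 183: |150 − 183| = 33 against 0, so Week 26 shows negative.
- Positive at an on-time Visit 4 on Day 24, negative at a re-examination on Day 30: |24 − 29| = 5 against |30 − 29| = 1, so Week 4 shows negative.

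**Does EOT (LOCF) rescue these?** Only if the positive exam is the subject's last nevi record in the period. A later negative exam replaces it.

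**Can such exams exist?** Protocol 9.4 provides for unscheduled visits and has their assessments entered in the eCRF. Neither document says how many included a nevi exam.

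**The case against.** The strongest reply is that the clinically relevant count mostly exists elsewhere. Protocol 10.9.4 states "Nevi of clinical concern must be recorded as AE". SAP 7.2.3.1 applies no visit window to such events: "An AE is classified as treatment emergent if it newly occurred on or after the first dose of study drug". The TEAE tables count each subject once per preferred term and show the arms separately. Clinically significant biopsy findings end treatment, and SAP 8.1.9 summarises suspensions and discontinuations. SAP 8.3 lists all safety data. An early termination exam will usually be the last record of its period and so appear in EOT (LOCF). The by-visit layout is what the protocol prespecified, and nevi are not a named adverse event of special interest, so the contrast with liver tests and QTc is not a contradiction.

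Most of this stands, and it keeps the point small. What can be missing from every summary table is a transient positive that was not judged to be of clinical concern. Even so, none of these outputs gives the number of subjects per arm who were ever positive on either item. The adverse event outputs have no nevi grouping comparable to the hepatic one, suspension counts do not count nevi findings, and a listing has to be counted by hand.

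Two further replies concern documents not available here. SAP 7 says analysis visits were confirmed at data review meetings, and a Day 22 nevi exam would be recognisable as Visit 4, since Visit 3 is allowed only on Days 10–20. The SAP nevertheless states no rule moving Day 22 to Week 4. A separate nevi assessment document may also define when the two items are completed at unscheduled exams.

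**Conclusion.** The concern holds, at low severity. As written, the plan gives no ever-positive count per arm for a named safety endpoint, and a positive exam can be absent from the nevi table. For scheduled exams the exposure is 1 of 15 allowed days at one visit. For off-schedule exams the number of subjects affected is unknown.

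This rests on Table 4 being applied as written and on the SAP 6.1 default governing SAP 8.3.6. It is an optional improvement to one descriptive table. It does not correct a bias in any efficacy result, and power and type I error are unaffected.

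**What to change.** In SAP 8.3.6, add one any-post-baseline row per subject for each of the two yes/no items, for DBT on SAF1 and for DBE on SAF2. Count a subject as positive if any scheduled, unscheduled or early termination evaluation in the period was positive, including evaluations outside a nevi window such as Day 22. Keep the by-visit rows.

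Moving the Week 2/Week 4 boundary so that Week 4 starts on Day 22 would place all 15 allowed Visit 4 days correctly. It would not recover displaced or off-schedule positives, so it does not replace the new row.

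The cost is a sentence in the SAP and one extra table block. The evaluations are already in the eCRF. SAP 1 foresees a Version 3.0 before the final database lock, which is a natural place for the change. If that version is already signed, the rows can be produced as a labelled supplementary output.

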7.4 Data Handling Convention for Missing Data

For missing of the onset time of the first prodromal symptom in in-clinic sunlight exposure test, impute from the formula of “end test time - start test time” as censoring time.

For the purpose of determining TEAE and AE duration, if the AE start date is incomplete, it will be imputed as follows:

- If the start date is completely missing, the start date will be equal to the date of the first dose date of study treatment. However, if the stop date is not missing and is before the date of the first dose of study treatment, then the stop date will be used instead and the AE will not be considered as TEAE.
- If the start day is missing, but the month and year are not missing and are equal to the month and year of the first study dose, then this event will be considered as TEAE.
- If the start day and month are missing, then the first day of the first month (January) will be used.

If an AE stop date is incomplete, it will be imputed as follows for the purpose of determining AE duration:

- If the AE stop date is completely missing, then the stop date will be equal to the subject's last observed date.
- If the Stop day is missing, but the month and year are not missing and are equal to the month and year of the last observed date, then stop date will be equal to last observed date.
- If the start day and month are missing, then the first day of the first month (January) will be used.

For the purpose of determining prior and concomitant use, if the medication start date is incomplete, then it will be imputed as follows:

- If the start date is completely missing, the start date will be equal to the first dose date. However, if the stop date is not missing and is before the first dose date, then the stop date will be used instead.
- If the start day is missing, the first day of the month will be used.
- If the start day and month are missing, then the first day of the first month (January) will be used.

If the medication stop date is partial, then it will be imputed as follows for the purpose of determining prior and concomitant use:

- If the stop date is completely missing and the medication is not ongoing, the stop date will be equal to the last dose date or date of completion/withdrawal, whichever is the latest.
- If the stop day is missing, the last day of the month will be used.
- If the stop day and month are missing, then the last day of the last month (December) will be used.

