4.1 Primary Week 26 Analysis

Primary Week 26 analysis will take place when the last subject completes Week 26 visit or follow-up period after DBT early termination and includes all subject data collected until then except for ongoing DBE or Follow up data. The available data in this analysis is as below;

Subject Type	Subject's Status on the date of LPLV for DBT			Primary Week 26 Analysis			
	DBT Period (26 weeks)	DBE Period (26 weeks)	Follow up (6 weeks)	DBT data	DBE data	Follow-up data	FU Type
A	Completed	Completed or Discontinued	Completed	X	X	X	DBE
B	Completed	Completed or Discontinued	No data	X	X		
C	Completed or Discontinued	No data	Completed	X		X	DBT
D	Completed or Discontinued	Ongoing in either DBE or FU / No data		X			

Note: X is "Included" in Primary W26 Analysis

After Week 26 database lock, the primary efficacy analysis will be conducted. No alpha adjustment for final analysis is needed, as this Week 26 efficacy analysis will be the primary efficacy analysis. The results will not be disclosed to any site-facing personnel or to any personnel directly involved with the conduct of the study. This detail was described in "MT-7117-G01 Blinding and Unblinding Plan Version 1.2 final.docx".

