7.1 Treatment Group Definitions and The Corresponding Analyzed Period Data

Two treatment group definitions for DBT data analysis and for DBE data analysis will be used as follows:

For DBT period data analysis

All DBT period data in all Subject type and Follow up period data in Subject type A, B, C and D in Section 4.1 will be analyzed with the below definition.

Treatment Group	Definition
MT-7117 [REDACTED]	Allocated to MT-7117 [REDACTED] group in DBT period
MT-7117 [REDACTED]	Allocated to MT-7117 [REDACTED] group in DBT period

Treatment Group	Definition
Placebo	Allocated to Placebo group in DBT period

For DBE period data analysis

All DBE period data and all Follow up period data in Subject Type A and B in Section 4.1 will be analyzed with the below definition.

Treatment Group	Definition
MT-7117 [REDACTED]	Allocated to MT-7117 [REDACTED] group in DBT period and Enrolled in DBE period.
MT-7117 [REDACTED]	Allocated to MT-7117 [REDACTED] group in DBT period and Enrolled in DBE period.
MT-7117 [REDACTED] (switched from Placebo)	Allocated to Placebo group in DBT period and switched to MT-7117 [REDACTED] group in DBE period.
MT-7117 [REDACTED] (switched from Placebo)	Allocated to Placebo group in DBT period and switched to MT-7117 [REDACTED] group in DBE period.

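### SAP 7.4 dates a year-only AE start to 1 January with no first-dose check, so such AEs in the year of first dose drop out of the TEAE tables; SAP 4.1, 5.2 and 7.1 also conflict on follow-up after the extension

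*SAP*

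**What the plan says.** **AE start dates.** SAP 7.4 states that its start-date imputation serves to determine TEAE status as well as AE duration. It has three rules:

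- No date at all: "If the start date is completely missing, the start date will be equal to the date of the first dose date of study treatment". The exception is a known stop date before first dose; the stop date is then used and the AE is not a TEAE.
- Day missing: if the month and year "are equal to the month and year of the first study dose, then this event will be considered as TEAE".
- Day and month missing: "If the start day and month are missing, then the first day of the first month (January) will be used".

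The date test in SAP 7.2.3.1 is "An AE is classified as treatment emergent if it newly occurred on or after the first dose of study drug".

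**Follow-up data.** SAP 7.1 analyses under the double-blind treatment (DBT) arms, as allocated, the "Follow up period data in Subject type A, B, C and D in Section 4.1". Under the double-blind extension (DBE) groups it analyses "All DBE period data and all Follow up period data in Subject Type A and B". The table in SAP 4.1 labels type A follow-up as DBE and type C follow-up as DBT. SAP 5.2 uses actual treatment received for safety and assigns a subject who took more than one treatment to the highest dose level, without saying over what period.

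**AE stop dates.** The third AE stop-date rule in 7.4 repeats the year-only sentence for start dates. The medication stop-date list in the same section has a proper rule: "If the stop day and month are missing, then the last day of the last month (December) will be used".

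**The concern.** The first two start-date rules refer to first dose and lean towards counting the event. The third does neither, so an AE with some date information is treated less conservatively than one with none. Nearly all the AE summaries in SAP 8.3.1 are built on TEAEs, including serious TEAEs, TEAEs leading to withdrawal and hepatic TEAEs. An event wrongly classed as not treatment emergent survives only in the listing of all AEs.

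The second issue is which column an AE falls in when it arises after the extension. Placebo subjects who enter the extension take MT-7117 for up to 26 weeks. If their later AEs, or their earlier ones, are put in the wrong column, the placebo comparison in the safety tables is blurred. Two programmers working from different sections could produce different tables.

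**Working it through.** **1. Year-only starts under the two rules together**

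Take an assumed first dose of 1 April 2021:

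- start recorded as 2021: imputed 1 January 2021, before first dose, not a TEAE;
- start completely missing: imputed 1 April 2021, a TEAE;
- start recorded as April 2021: a TEAE.

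Over every possible first-dose date, a year-only AE in the same calendar year fails the test on 364 of 365 dates (365 of 366 in a leap year). Only 1 January passes. A year-only start in the following year is imputed after first dose and remains a TEAE.

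**2. Illustrative size**

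The plan gives no figure to reproduce. Let first dose fall on day d of a 365-day year. The DBT period has 182 days (SAP Table 2). DBT days in the dosing year = min(182, 366 − d). The share of year-only DBT-period AEs that is misclassified, assuming onsets spread evenly over the period, is:

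- d = 2 to 184 (2 January to 3 July): 182/182 = 100%;
- d = 275 (2 October): 91/182 = 50%;
- average over uniform first-dose dates: the sum over d = 2 to 365 is 183 × 182 + (181 × 182)/2 = 33,306 + 16,471 = 49,777, and 49,777/(365 × 182) = 49,777/66,430 = 74.9%.

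**3. What a first-dose default would cost, same assumptions**

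- Screening lasts up to 42 days (SAP 3.2.1). Screening days in the dosing year = min(42, d − 1), summing to 14,427. DBT days over all 365 dates sum to 49,777 + 182 = 49,959. The pre-dose share is 14,427/(14,427 + 49,959) = 22.4%.
- For a subject who enters the extension, extension days in the dosing year = max(0, min(182, 184 − d)), summing to 16,835. Their share of post-dose treatment days is 16,835/(16,835 + 49,959) = 25.2%.

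**4. Follow-up, section by section**

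| Type in 4.1 | Follow-up at the Week 26 analysis (4.1) | In 7.1 DBT list | In 7.1 DBE list |
|---|---|---|---|
| A (extension ended, follow-up complete) | Yes, labelled DBE | Yes | Yes |
| B (extension ended, no follow-up data) | None | Yes | Yes |
| C (no extension, follow-up complete) | Yes, labelled DBT | Yes | No |
| D (extension or follow-up ongoing, or no data) | None | Yes | No |

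Type A is assigned twice, and its DBT entry contradicts 4.1. Types are fixed by status on the date of the last DBT visit. Unless they are redefined for the final analysis, a type D subject then in the extension has later follow-up named only under the DBT arms.

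Visit-based data are already separated: the visit-window tables in SAP 7.3 and the reporting tables in 9.3 distinguish Week 32 from Week 58 follow-up. AEs have no visit window, the TEAE rule has no end date, and SAP 8.3 assigns DBT and DBE data to SAF1 and SAF2 without naming follow-up. Protocol 12 collects AEs until 6 weeks after the last treatment visit.

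For a former placebo subject there are then two possible outcomes:

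- If the 7.1 allocation definition prevails, an AE after the active extension can be tabulated under Placebo. AE tables count a subject once per term, so each subject with a new term adds 1/61 = 1.6 percentage points, taking about 61 per arm (Protocol 8.1).
- If the 5.2 highest-dose rule prevails over the whole study, the subject moves to MT-7117, and the placebo-period data can move too.

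At the Week 26 analysis only type A subjects can be affected, because data are included "except for ongoing DBE or Follow up data".

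**The case against.** On year-only starts, the best reply is that the set may be empty. Protocol 12.7 has AEs asked about at each visit and the eCRF records date of onset, so both day and month will seldom be unknown. The rule is the same for every arm, and misclassified events stay in the listing. The averages also assume uniform first-dose dates, while Protocol 8.1 describes rapid enrolment in the last few months. All of this limits the size. It does not make the rule consistent with its neighbours, and no other section overrides it.

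On follow-up, a reader might infer from 7.1 that the Placebo column of the DBT tables will contain events that arose after MT-7117. The documents do not establish that. SAP 5.2, read literally, would place such a subject under MT-7117, and no passage says whether 5.2 or 7.1 governs. The FU Type column in 4.1 and the visit tables point to the intended split, so the 7.1 list is probably a slip. What stands is an unresolved conflict between three sections.

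The stop-date slip affects AE duration only, and no summary listed in SAP 8.3.1 uses AE duration. The treatment duration named there is a different variable.

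**Conclusion.** The year-only start rule is wrong as written. It excludes from the TEAE tables any AE dated only by the calendar year of first dose, for every first dose except 1 January. The number of such AEs is unknown, probably small and possibly zero. The 74.9% is an illustrative share of that unknown number, resting on uniform first-dose dates and onsets spread evenly over the DBT period. It should not be read as a share of all AEs.

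On follow-up, the finding is that SAP 4.1, 5.2 and 7.1 must be reconciled, since either misplacement is possible depending on which rule is followed. The number of former placebo subjects concerned is not stated. The stop-date sentence is a wording correction. No efficacy analysis is affected by any of the three.

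**What to change.** - **SAP 7.4, AE start.** For a year-only start in the calendar year of first dose, impute the first-dose date and class the AE as a TEAE, unless the stop date is before first dose. This is how 7.4 already treats completely missing dates.
- **SAP 7.1 and 5.2.** Correct the DBT list so that follow-up of subjects who entered the extension goes only to the DBE groups, and follow-up of subjects who did not goes to the DBT arms. Apply the same split to type D subjects at the final analysis. State in 5.2 that the highest-dose rule applies within a period.
- **SAP 7.4, AE stop.** Replace the repeated sentence: for a year-only stop, use the earlier of 31 December and the last observed date.

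The cost is SAP wording and derivation code, with no new data. A few screening AEs may count as TEAEs, and a few extension-period AEs may be dated to the DBT period; the 22.4% and 25.2% above indicate the scope under the stated assumptions. Assigning the period case by case would avoid the second effect, but it would not be a pre-specified rule, and the AE eCRF fields listed in Protocol 12.7 include no reporting visit. SAP 7 describes the data review meetings as already held, so any tables already produced would need a rerun and the change should be documented.
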